8.2 Concomitant Therapy

Doses of any concomitant AEDs, including CLB, must have been stable for at least four weeks prior to screening and must remain stable throughout the blinded phase of the study. If there are symptoms of toxicity suspected to be from a drug interaction, the investigator may adjust GWP42003-P/placebo or the CLB or other AEDs after discussion with the medical monitor.

The use of rescue medication is allowed if necessary. The use of oxygen may be considered as rescue medication if used as required. Any medication, other than the IMP, taken during the study must be recorded on the Case Report Form (CRF).

Any non-pharmacological therapies (e.g., ketogenic diet, VNS) must also be stable up to four weeks prior to baseline and throughout the duration of the study.

8.3 Prohibited Therapy During Study Period

The following medications are prohibited for the duration of the study starting from acquisition of patient consent. However, any patients taking these medications after screening should not be withdrawn from the study unless there are safety concerns. If applicable, the possible effects of these medications on the primary endpoint will be considered.

- Any new medications or interventions for epilepsy (including ketogenic diet and VNS) or changes in dosage.
- Patients should not take any more than three AEDs inclusive of CLB.
- Recreational or medicinal cannabis or synthetic cannabinoid based medications (including Sativex) within three months prior to or during the study.

If any other IMP is taken as part of a clinical trial within twelve weeks of the screening visit or during the study, the patient must be withdrawn from this study.

8.4 Compliance in Investigational Medicinal Product Administration

Patients or their caregivers will record the total volume of IMP, administered on each treatment day, using the paper diary and will be asked to return all IMP (used and unused) at each subsequent visit. The site will check the returned IMP against the

usage recorded in the diary and the projected usage. Any discrepancies will be discussed with the patient/caregiver and documented accordingly within the patient's source documents.

The investigator must inform GW promptly of all missing or unaccountable IMP.

Records of IMP accountability will be maintained according to [Section 5.3.4](#).

8.5 Access to Blinded Treatment Assignment

The identity of IMP assigned to patients will be held by the IVRS. The principal investigator (PI) at each center is responsible for all trial-related medical decisions and is responsible for ensuring that information on how to access the IVRS is available to the relevant staff in case of an emergency and unblinding is required. A patient's treatment assignment must only be unblinded when knowledge of the treatment is essential to make a decision on the medical management of the patient. Unblinding for any other reason will be considered a protocol deviation.

The investigator is encouraged to contact GW to discuss the rationale for unblinding. However, to prevent delays to the investigator or medical personnel responding to a potentially emergent situation, unblinding of study medication will not be dependent upon the investigator receiving approval from GW (i.e., the investigator will be able to obtain the code break information independent of contacting GW).

If the investigator does unblind they must contact GW within one working day of the event and must document the time, date and reasons for unblinding in the patient's CRF.

9. STUDY PROCEDURES

A list of the required study procedures is provided in the subsections that follow; refer also to the Schedule of Assessments in [APPENDIX 1](#). Assessments or tests that are not done and examinations that are not conducted must be reported as such on the CRFs.

The location of the source data for the following procedures will be documented, per center, in a signed ‘Source Data Verification Plan’, for further details see [Section 16.2](#).

9.1 Study Procedure Listing

9.1.1 Contraception

To be eligible for the study, the patient must have agreed that if they or their partner are of child-bearing potential they are willing to use highly effective contraception for the duration of the study and for three months thereafter. A highly effective method of birth control is defined as those which result in a low failure rate (i.e., less than 1% per year) when used consistently and correctly such as combined or progesterone only oral contraceptives, intrauterine device, intrauterine hormone-releasing system, bilateral tubal occlusion, vasectomized partner or sexual abstinence⁶. Abstinence, as referenced above, is only acceptable as true abstinence: when this is in line with the preferred and usual lifestyle of the patient; periodic abstinence (e.g., calendar, ovulation, symptothermal, post-ovulation methods) and withdrawal are not acceptable methods of contraception. The use of hormonal contraception must be supplemented with a barrier method (preferably male condom).

9.1.2 Informed Consent

Adult patients with an adequate level of understanding must personally sign and date the IRB/EC approved ICF(s) before any study specific procedures are performed or any patient related data is recorded for the study. For adult patients with an insufficient level of understanding of what is proposed, only personal legal representative consent will be sought. The informed consent process should be documented within the patient notes.

GW requires a physician to be present for consent and to also sign the ICFs.

9.1.3 Demographics

Patient demographics will be recorded at Visit 1. The following information will be obtained for each patient: date of birth, gender and race (if allowed per local regulations).

9.1.4 Medical History

Relevant, significant medical history (including seizure information since diagnosis, history of epilepsy-specific genetic testing and all prior AEDs taken) will be obtained during Visit 1 and is defined as any condition or disease that:

- May affect the condition under study.
- Is ongoing on entry into the study.

9.1.5 Concomitant Medication

Details of all current and recent medication (i.e., taken within the previous 28 days) including AEDs will be recorded at the screening visit (Visit 1) and reviewed at each subsequent visit. AEDs used during the study should be maintained at a stable dose. Any changes in concomitant medication during the study must be recorded in the CRF at study visits. Patients should stop taking any prohibited therapy prior to the screening visit, as defined in [Section 8.3](#).

9.1.6 Physical Examination

A physical examination will be performed at the screening visit (Visit 1) to ensure that the patient is eligible to enter the study. To ensure patient safety, further physical examinations will be performed at every hospital visit. Physical examinations will include height (at screening) and body weight measurements.

9.1.7 Vital Signs

Vital sign measurements, taken after five minutes rest in a sitting position, will be completed alongside the physical examination at all visits. Postural BP will be assessed after five minutes in supine position and, if possible, two minutes in standing position. The pulse rate must also be measured as part of the vital sign assessments. BP and pulse rate must be recorded using the same arm throughout the study.

9.1.8 12-Lead Electrocardiogram

An ECG will be performed, after five minutes in supine position, at all hospital visits. A physician must review the ECG and any abnormal findings considered to indicate significant medical history or AEs must be recorded appropriately in the CRF. Additional ECG measurements can be taken at any time during the study, if clinically indicated.

9.1.9 Clinical Laboratory Sampling

Laboratory tests will be undertaken at all hospital visits and will include hematology, biochemistry, and urinalysis (provided urine can be obtained, with the exception of

screening where a urine sample for THC screen must be obtained). A serum alcohol test will be performed at Visits 1, 2 and 4. A serum pregnancy test (if appropriate) will also be performed at Visit 1.

Urine samples for biochemistry will be analyzed at the study center by use of a dipstick with any relevant findings being sent for further laboratory based urinalysis (urinalysis, microscopy, culture and sensitivity, as applicable).

The investigator and study monitor will be provided with a list of the normal ranges used by the testing laboratory for all variables assayed during the study and a statement of accreditation (or similar) for the laboratory. Clinical laboratory sample parameters are detailed in [Table 9.1.9-1](#).

Table 9.1.9-1 Hematology, Biochemistry, Urinalysis and THC Screen

Biochemistry (serum)	Hematology (whole blood)	Urinalysis (urine)	Pregnancy Test	THC screen (urine)
Alanine aminotransferase (ALT)	Hematocrit	Bilirubin	Serum	THC
Albumin	Hemoglobin	Blood		
Alkaline phosphatase	Mean cell volume	Glucose		
Aspartate aminotransferase (AST)	Mean corpuscular hemoglobin	Ketones		
Calcium	Platelets	Nitrites		
Creatinine	Red blood cell count	pH		
Estimates of glomerular filtration rate	White blood cell count with automated differential	Protein		
Gamma-glutamyl transferase		Specific gravity		
Glucose		Urobilinogen		
HDL-cholesterol				
Potassium				
Prolactin				
Prothrombin time (plasma)				
Sodium				
Total bilirubin (TBL)				
Total protein				
Urea (BUN)				
Triglycerides				

All laboratory results will be reviewed and the reports signed by an investigator. Any results considered to be of clinical significance must be addressed and followed up as clinically appropriate. See [Section 12.8](#) for guidance on evaluation of potential drug-induced liver injury. All laboratory results considered by the investigator to represent an AE must be documented on the CRF.

Repeat samples will be taken, if required, for clinical follow up or if the sample is lost or damaged. Any abnormal end of treatment clinical laboratory result of clinical significance must be repeated at regular intervals until it returns to normal, or until an

investigator is satisfied that the abnormality is not related to the IMP and needs no further investigation.

Sample volume requirements and processing procedures will be detailed in a separate laboratory manual. The patient/caregiver must be advised that it may not be safe for them to undertake further blood tests within one month of any study-related blood draws and to inform the investigator if they suffered any blood loss in the four weeks prior to screening.

9.1.10 Pharmacokinetic Analyses

The plasma concentration/time curves of CLB, N-CLB, VPA, STP, LEV and TPM will be assessed at Visit 2 (Day 1 and Day 2) and CLB, N-CLB, VPA, STP, LEV, TPM, CBD, CBD major metabolites, THC and THC major metabolites at Visit 4 (Day 33 and Day 34). Patients will be given their daily dose of CLB at a scheduled time during Visit 2 and Visit 4 and the GWP42003-P/placebo immediately afterwards (Visit 4 only) to facilitate the accurate timing of blood samples required for PK analysis. Blood samples will be taken by either direct venipuncture or an indwelling cannula inserted into a forearm vein at the following times: Pre-dose and, 15 minutes, 30 minutes, 1 hour, 1.5 hours, 2 hours, 4 hours, 6 hours, 12 hours and 24 hours after dosing. The timing of each PK sample will be relative to the morning dose of CLB.

The pre-dose blood sample will be taken within 30 minutes prior to dosing. The allowable window for post-dose blood sample collection is \pm 2 minutes up to and including 1 hour post-dose, \pm 5 minutes from 1.5 hours up to and including 6 hours post-dose and \pm 1 hour at 12 hours and 24 hours post-dose.

In the event of an AE that, in the opinion of the investigator, is related to a concomitant AED, additional blood samples may be collected.

Analysis of all PK samples will be conducted at a central clinical laboratory. Sample volume requirements and processing procedures will be detailed in a separate laboratory manual.

9.1.11 Genetic Testing

Genetic testing will only be conducted if specific consent is obtained from the participant or their legal representative. There is a separate ICF for this.

Genetic testing will be conducted to look at the CYP450 genes, with particular focus on CYP 2C19 and CYP 3A4, involved in the metabolism of AEDs and GWP42003-P.

9.1.12 Columbia Suicide Severity Rating Scale

The C-SSRS is to be completed by the investigator or his/her qualified designee at all hospital visits. Qualified designee is defined as physician, osteopath, nurse practitioner, clinical psychologist or physician's assistant who is licensed and has completed the C-SSRS training within the last two years. It is a brief standardized measure that uniquely assesses the essential information (behavior, ideation, lethality and severity) and distinguishes between suicidal occurrences and non-suicidal self-injury. The survey should be completed by the same assessor, where possible, throughout the study.

If the investigator or his/her qualified designee feel that the patient is either unable to answer the questions presented in C-SSRS, or that the questions are causing undue stress to the patient, the questionnaire may be skipped and this must be documented in the patient notes.

9.1.13 Patient Diary

Patients or their caregivers will be instructed on how to complete a paper diary and will be asked to record information daily in it. The number and type of seizures as well as information on AEs, concomitant AEDs and rescue medication will be collected each day from screening (Visit 1) until completion of dosing or withdrawal. Information on IMP intake will also be recorded each day from enrollment (Visit 2) until completion of dosing or withdrawal.

9.1.14 Investigational Medicinal Product Accountability

GWP42003-P/placebo will be dispensed at each of the following visits during the blinded phase:

- Visit 2 (Day 2)
- Visit 4 (Day 34)

IMP will be dispensed at each of the following visits for patients entering the OLE:

- Visit 5 (Two weeks)
- Visit 6 (One month)
- Visit 7 (Two months)
- Visit 8 (Three months)
- Visit 9 (Six months)
- Visit 10 (Nine months)
- Visit 11 (12 months)

Patients will be asked to return all IMP (used and unused) to each relevant visit (Visits 2 to 12). The site will check the returned IMP against the usage recorded in the paper diary. Any discrepancies will be discussed with the patient/caregiver and documented accordingly within the patient's source documents.

9.1.15 Adverse Events

Any adverse changes in the patient's medical condition, following completion of the consent form by the patient, will be recorded on the CRF as AEs, questioning the patient further if necessary. All AEs* occurring during the study, whether or not attributed to the IMP, observed by the investigator or reported by the patient will be recorded in the CRF.

* For the patient's expected seizure types, these do not routinely require documentation as AEs. However, any worsening, including change in the pattern or severity of seizures, must be documented as an AE.

Serious Adverse Events (SAEs) must be reported to GW Pharmacovigilance Department (PWD) within 24 hours of discovery or notification of the event, and recorded in the CRF.

Refer to [Section 12](#) for definitions, procedures and further information.

Inpatient hospitalizations that are, in the investigator's opinion, due to epilepsy will be recorded in the patient's CRF and through the SAE reporting process.

Refer to [Section 9.1.16.1.1](#) for the list of 'Triggering AEs of Interest' associated with monitoring of drug abuse liability.

9.1.16 Monitoring of Drug Abuse Liability

There are two triggers that will require the investigator or study coordinator to discuss abuse potential signals with the patient or their caregiver. These are either AEs of interest that may be reported by the patient/caregiver, or drug accountability issues regarding overuse of the IMP or missing bottles. Different questionnaires will be completed by the site depending upon which trigger occurs (see [Figure 9-1](#)).

Irrespective of the above, all patients/caregivers will be interviewed at their final dosing visit (Visit 5 or Visit 12) or withdrawal visit and a Study Medication Use and Behavior Survey will be completed by the investigator or study coordinator.

Investigators and study coordinators will be provided with training on how to complete and perform the processes outlined in this section. This training must be completed and documented by the relevant site staff prior to implementation at site.

9.1.16.1 Monitoring of Adverse Events

AE information will be collected according to [Section 9.1.15](#).

9.1.16.1.1 List of 'Triggering Adverse Events of Interest'

During the collection of AEs, if the patient reports an AE consistent with any of the following categories, then the investigator or study coordinator is required to complete an additional Supplemental Adverse Event Form and a Site Classification Form (investigator only) following further discussion of the event(s) with the patient or their caregiver. The categories are:

- Euphoria or inappropriate elation.
- Inappropriate laughter or exhilaration.
- Mood changes.
- Drunk, high or intoxicated.
- Hallucinations (visual or auditory), dissociations, disorientation, agitation.
- Disturbance in cognition, memory, or attention.
- Drug abuse.
- Drug withdrawal or drug withdrawal syndrome.
- Addiction.
- Overdose.
- Misuse of IMP.
- Thoughts of suicide, attempted suicide or suicide.

An AE that is consistent with the above categories will be known as a 'triggering AE of interest' for the purposes of this study.

9.1.16.1.2 Supplemental Adverse Event Form

This form consists of 15 questions regarding the AE and use of IMP. It is completed as part of an interview with the patient/caregiver when a triggering AE of interest is reported. It is important that this is completed by a trained investigator or study coordinator with the patient/caregiver present. The answers on the Supplemental Adverse Event Form will then be transcribed into the patient's CRF for the study. If the Supplemental Adverse Event Form cannot be completed at the time the triggering AE of interest is reported, then the site should contact the patient/caregiver to obtain the required answers as soon as possible.

9.1.16.2 Monitoring Drug Accountability Discrepancies

Any time after enrollment until final collection of study data, drug accountability discrepancies are monitored as follows:

- At routine drug accountability collection times, the site personnel will collect the IMP clinical supplies and make sure the usage is in line with the expectations reported within the paper diary.
- At any time that the site is informed by the patient/caregiver about any overuse of IMP, suspected misuse, abuse, or diversion.

9.1.16.2.1 List of 'Triggering Drug Accountability Discrepancies'

If there are any discrepancies in drug accountability as outlined by the criteria below, known as 'triggering drug accountability discrepancies', then the trained investigator or study coordinator will complete a Supplemental Drug Accountability Form and Site Classification Form (investigator only) following further discussion of the event(s) with the patient/caregiver. The triggering drug accountability discrepancies are as follows:

- Missing bottle(s).
- Compliance issues where one or more bottles are used compared to what was the expected use, according to the paper diary.
- Returned IMP supply with evidence of tampering.
- Greater than the target daily dose as recorded in the paper diary.

9.1.16.2.2 Supplemental Drug Accountability Form

This form consists of eight questions regarding various aspects of drug accountability and patient usage. It is completed as part of an interview with the patient/caregiver when a triggering drug accountability discrepancy is identified. It is important that this is completed by a trained investigator or study coordinator with the patient/caregiver present. The answers on the Supplemental Drug Accountability Form will then be transcribed into the patient's CRF for the study. The accountability reporting procedures will still occur. If the Supplemental Drug Accountability Form cannot be completed at the time the triggering drug accountability discrepancy is identified, then the site should contact the patient/caregiver by telephone to obtain the required answers as soon as possible (Note: IMP refers to GWP42003-P or placebo, not other concomitant medications).

9.1.16.3 Site Classification Form

The investigator should review the applicable Supplemental Adverse Event Form or Supplemental Drug Accountability Form, and then complete the Site Classification Form. For each Supplemental Adverse Event Form or Supplemental Drug Accountability Form completed, there should be an associated Site Classification Form.

The Site Classification Form requires the investigator to assign the finding to an appropriate classification and then to also assign the possible relationship to the IMP. The investigator is also required to indicate the level of the certainty of the classification. The answers from the Site Classification Form will then be transcribed into the patient's CRF for the study.

9.1.16.4 Study Medication Use and Behavior Survey

This form consists of 18 questions regarding the use of the IMP. The trained investigator or study coordinator will complete this survey as an interview with the patient/caregiver at the final dosing visit (Visit 5 or Visit 12) or withdrawal visit. The answers on the Study Medication Use and Behavior Survey will then be transcribed into the patient's CRF for the study.

The Study Medication Use and Behavior Survey will be completed for all patients in the study and not only those that have reported a triggering AE or drug accountability discrepancy.

9.1.16.5 Adjudication Committee — Assessment of Abuse Potential of GWP42003-P

A formal Adjudication Committee will be appointed and assigned to this initiative to classify triggered cases. The Adjudication Committee will meet on a periodic basis to review and assess all of the information collected on triggered cases. Only data from patients who have completed the study will be assessed.

A detailed charter will be agreed, which will describe the roles, responsibilities and duties of the members of Adjudication Committee. The Committee will review all of the information collected in the process and in the assessment of the abuse potential of GWP42003-P, such as:

[figure not shown]
- All triggering AE information.
- Supplemental Adverse Event Form (if applicable).
- All triggering drug accountability discrepancies.
- Supplemental Drug Accountability Form (if applicable).
- Site Classification Form.
- Study Medication Use and Behavioral Survey.
- Additional information from site(s) as requested by the Committee.

The Adjudication Committee will assess all of the information. It will form a position on the classification of each event and will write a study-related report, detailing the conclusions and recommendations.

The overall process is summarized in [Figure 9-1](#).

Figure 9-1

**Flow Diagram for Identifying and Evaluating Clinical Trial
Adverse Event Data Through Systematic Categorization
Tabulation and Analysis which can Illuminate an Abuse
Potential Signal**

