Monitoring of Drug Abuse Liability

During the routine collection of AEs in this study, if AEs are reported which can illuminate an abuse potential signal (specific AEs detailed in Section 9.1.16.1.1), then the investigator or study coordinator is required to complete an additional Supplemental Adverse Event Form and a Site Classification Form (investigator only) following further discussions of the event(s) with the patient/caregiver.

The second trigger that will require the investigator or study coordinator to discuss abuse potential signals with the patient/caregiver is drug accountability issues regarding overuse of the IMP or missing IMP bottles.

Irrespective of the above, all patients/caregivers will be interviewed at their final dosing visit or withdrawal visit and a Study Medication Use

	
and Behavior Survey will be completed by the investigator or study coordinator.
 
A formal Adjudication Committee will be appointed and assigned to this initiative to classify triggered cases. The Adjudication Committee will meet on a periodic basis to review and assess all of the information collected on triggered cases.

Statistical Considerations	
Plasma concentration data will be analyzed to estimate PK endpoints C_{max}, t_{max}, $AUC_{(0-t)}$, $AUC_{(0-\infty)}$ and $t_{1/2}$ of the following analytes: CLB, N-CLB, VPA, STP, LEV, TPM, CBD, CBD major metabolites, THC and THC major metabolites.
 
In order to assess whether the presence of CBD alters the PK profile of CLB or N-CLB, a standard 90% confidence interval (CI) approach for the between group ratios of geometric means of C_{max} $AUC_{(0-t)}$, and $AUC_{(0-\infty)}$ will be done on logarithm scale using a linear mixed effect model with treatment (CLB or CLB+GWP42003-P) as a fixed effect and subject as a random effect. The no-effect boundary will be set between 0.5 and 2.0 and if the 90% CI for the ratio of the geometric means of a PK variable falls within the interval [0.5, 2.0], a lack of meaningful effect will be declared.
 
Descriptive summaries (means and standard deviations or counts [%] as appropriate) will be presented for all secondary endpoints (adverse events, laboratory data, vital signs, physical examination, C-SSRS and seizure frequency) for each phase of the study.

Sponsor	
GW Research Ltd [name] United Kingdom

Figure 1-1 **Study Design and Treatment Schema**

[figure not shown]

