10. WITHDRAWAL

In accordance with the Declaration of Helsinki³¹, the FDA regulations relating to good clinical practice (GCP) and clinical trials^{32,33,34}, the EU Clinical Trials Directive (2001/20/EC)³⁵ and/or other applicable regulations, a patient has the right to withdraw from the study at any time and for any reason without prejudice to his or her future medical care by the physician or at the institution.

The patient must be withdrawn from the study if any of the following apply:

- Administrative decision by the investigator, GW, or a Regulatory Authority.
- Pregnancy.
- Protocol deviation that is considered to potentially compromise the safety of the patient.
- Withdrawal of patient consent.
- Withdrawal of legal representative consent.
- Lost to follow up.
- ALT $> 3 \times$ ULN or AST $> 3 \times$ ULN **and** (TBL $> 2 \times$ ULN **or** INR > 1.5).
- ALT or AST $> 3 \times$ ULN with the appearance of fatigue, nausea, vomiting, right upper quadrant pain or tenderness, fever, rash, and/or eosinophilia ($> 5\%$).
- ALT or AST $> 8 \times$ ULN.
- ALT or AST $> 5 \times$ ULN for more than two weeks.
- Any other IMP is taken as part of a clinical trial during the study.

- Significant change in QTcB (> 60 msec) from the previous ECG or absolute QTcB of > 500 msec.

Patients may also be withdrawn from the study for any of the following:

- Patient non-compliance.
- AE, which in the opinion of the investigator, would compromise the continued safe participation of the patient in the study.
- Any evidence of drug abuse or diversion.
- Suicidal ideation or behavior of type four or five during the treatment period, as evaluated with the C-SSRS.

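### The abuse-liability committee is limited to study completers, which contradicts its own remit and, read literally, drops triggered cases in patients who withdraw

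*Protocol*

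**What the plan says.** Abuse liability is one of the secondary safety and tolerability endpoints (protocol version 4, section 4.1.2). Section 9.1.16 describes how it is monitored. Certain adverse events and certain drug-accountability discrepancies act as triggers. A trigger leads to a supplemental form and an investigator's site classification, and a committee then classifies the case.

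Section 9.1.16.5 gives the committee's remit: "The Adjudication Committee will meet on a periodic basis to review and assess all of the information collected on triggered cases". The next sentence reads: "Only data from patients who have completed the study will be assessed". The synopsis repeats the remit, saying that the committee will "meet on a periodic basis to review and assess all of the information collected on triggered cases", but does not carry the restriction.

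Data collection is not limited to completers. Section 9.1.16 says that "all patients/caregivers will be interviewed at their final dosing visit (Visit 5 or Visit 12) or withdrawal visit", and section 9.1.16.4 requires the survey for every patient in the study.

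Section 10 lists grounds on which a patient may be withdrawn. Among them are:

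- "Any evidence of drug abuse or diversion"
- "AE, which in the opinion of the investigator, would compromise the continued safe participation of the patient in the study"
- "Suicidal ideation or behavior of type four or five during the treatment period, as evaluated with the C-SSRS"

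**The concern.** The restriction is operative text in the current protocol, and nothing elsewhere in the protocol brings withdrawn patients back into the committee's review. The events the committee exists to classify overlap with the events for which a patient may be taken out of the study. Whether a case is adjudicated would then depend partly on how serious the abuse signal was. That is selection on the outcome, and it pulls in one direction: cases serious enough to end participation are the ones that drop out.

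At stake is the committee's classification and its written report on abuse potential. The committee is the only central adjudication of these cases that the protocol describes, and section 14 plans no independent data safety monitoring committee. The rule also departs from section 13.3.1, which makes all treated subjects the primary set for all safety endpoints.

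**Working it through.** The protocol gives no figure on this point, so there is nothing to reproduce. The check is a comparison of passages, followed by an illustration of direction.

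**Step 1. Remit against restriction.** Section 9.1.16.5 and the synopsis both give the committee all information on triggered cases. One sentence in 9.1.16.5 removes every patient who did not complete. Both cannot apply to a triggered patient who withdraws.

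**Step 2. Collection against use.** The survey is taken at the withdrawal visit (9.1.16, 9.1.16.4). The supplemental forms are completed when a trigger is reported or identified, or as soon as possible afterwards (9.1.16.1.2, 9.1.16.2.2). So the material on a withdrawn patient would normally exist, and the restriction prevents the committee from assessing it.

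**Step 3. Overlap of triggers and withdrawal grounds.**

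| Withdrawal ground (section 10) | Matching trigger or monitoring | Overlap |
|---|---|---|
| Abuse or diversion (may) | Drug abuse and misuse are triggering events (9.1.16.1.1); reports of suspected misuse, abuse or diversion are monitored (9.1.16.2) | Close |
| Type 4 or 5 suicidality (may) | "Thoughts of suicide, attempted suicide or suicide" (9.1.16.1.1) | Close |
| Adverse event that makes participation unsafe (may) | Any listed category, if the event falls in one | Partial |
| Lost to follow-up (must) | Missing bottles (9.1.16.2.1), if the patient disappears with supply | Possible |

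The first three grounds are discretionary, so a triggered patient can stay and still be reviewed. One exclusion is certain: suicide is itself a listed trigger, and a patient who dies cannot complete the study.

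**Step 4. Does the protocol treat withdrawal as a form of completion?** The Definition of Terms has no entry for completing the study. Related wording keeps the two apart. The end-of-treatment entry names completion and withdrawal as alternatives, the diary rule in 9.1.13 does the same, and 13.5.1 separates patients completing the study from those who stopped IMP early.

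**Step 5. Direction of the effect (illustration only).** Let *n* be the patients on active drug, *p* the chance that a patient has a triggered case, and *w* the share of triggered patients who withdraw. With patients independent, the chance that the committee sees at least one triggered case is 1 − (1 − *p*(1 − *w*))^*n*. From 20 patients at 4:1 (sections 13.1 and 7.2), *n* = 20 × 4/5 = 16 in the blinded phase. Both *p* and *w* are assumptions; the protocol gives neither.

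| *p* | *w* = 0 (all reviewed) | 25% | 50% | 75% | 100% |
|---|---|---|---|---|---|
| 5% | 0.560 | 0.457 | 0.333 | 0.182 | 0 |
| 10% | 0.815 | 0.713 | 0.560 | 0.333 | 0 |
| 20% | 0.972 | 0.926 | 0.815 | 0.560 | 0 |

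For example, at *p* = 10%, 1 − 0.90^16 = 0.815 with everyone reviewed, and 1 − 0.95^16 = 0.560 if half of the triggered patients withdraw. Placebo patients who enter the extension also receive active drug, so up to 20 may be exposed; with *n* = 20 the same pair is 0.878 and 0.642. The table shows that the rule can only reduce what the committee sees. It does not estimate by how much in this trial.

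**The case against.** The best counter-argument is that the sentence is a timing rule. It follows directly on the statement that the committee meets periodically, so it may mean only that no case is adjudicated while the patient is still in the study. The rest of the section fits that reading: the committee is to consider all triggering information and the survey, and to take a position on each event. This reading is possible, but the sentence does not state it, and the protocol's habit of naming completion and withdrawal separately counts against it. Even if timing was intended, a committee working from the words as they stand could exclude withdrawn patients.

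A second argument is that the evidence survives. That is right. Adverse events are summarised on all treated subjects (13.3.1, 13.6.4.2). The investigator's classification, causality and certainty for each trigger go into the CRF (9.1.16.3). Section 12.2 gives drug dependency or abuse as an example of an event usually considered serious. What is lost is the committee's own classification and report.

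Two stronger inferences are tempting, and the documents support neither. A reader might infer that the rule removes precisely the abuse cases and makes the report wrong by construction. The relevant withdrawals are mostly discretionary, triggered patients who complete are still reviewed, and patients who leave for unrelated reasons are dropped too. A reader might also put a count on the loss, for instance 10% to 30% of 20, or 2 to 6 patients. Those withdrawal rates are not in the protocol, and the count covers all withdrawals. A patient who leaves because of pregnancy, liver enzymes or QTcB may have no triggered case at all.

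Finally, Figure 9-1 and the committee charter are not available here. Neither can be assumed to repeat the restriction or to cure it.

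**Conclusion.** The point stands as an internal contradiction that, on its literal reading, biases the committee's output. The completers-only sentence cannot be squared with the remit in its own section and in the synopsis, and it sits badly with the survey at the withdrawal visit. If it is followed as written, triggered cases in withdrawn patients are not adjudicated, and the committee's report on abuse liability would tend to understate the signal.

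The number of cases affected cannot be derived from the protocol and may be zero. The direction rests on the overlap between the trigger lists and the withdrawal grounds, and on at least some triggered patients being withdrawn. Abuse liability is one of several descriptive secondary safety parameters in a 20-patient PK study, so the primary PK conclusions are untouched. The sentence should still be corrected, because in so small a trial a single unadjudicated case matters.

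**What to change.** Replace the sentence in section 9.1.16.5 with:

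> *All triggered cases in all patients who received at least one dose of GWP42003-P or placebo will be adjudicated, whether or not the patient completed the study; cases are submitted once the patient has completed or withdrawn.*

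Put the same rule in the committee charter. This removes the contradiction with the synopsis, brings the review population into line with the Safety set, and keeps a timing rule if that was the purpose. The cost is one sentence in each of two documents. No new data collection is needed, because the supplemental forms, site classifications and survey are already required for these patients.
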